3.1 Investigator Selection

In order for investigators to participate in the study, they must meet the following criteria:

- A qualified physician, such as an interventional radiologist, vascular surgeon or cardiologist
- Qualified to practice medicine at NYU
- Able to provide adequate time and staff support for the study
- Able to comply with the protocol and legal contract for the study
- At an institution that has access to a registered IRB.

3.2 Investigator Responsibilities

The investigator is responsible for protecting the rights, safety, and welfare of subjects. An investigator must conduct the investigation in accordance with the study contract with the sponsor of the study, the protocol, the FDA regulations that apply to this study including 21 CFR 50 [Protection of Human Subjects] and 21 CFR 56 [Institutional Review Boards (IRB)], and any conditions of approval imposed by an IRB.

The Principal Investigator (PI) and other staff conducting the study will be trained prior to performing any activities for the study. Should the PI choose to delegate study related tasks to qualified personnel under their supervision, they must be trained on the study relative to the tasks that have been assigned to them.

4. Methodologies

4.1 Study Design

The study design is a single-center, prospective, randomized control trial to assess the performance of OAS and DAS for removal of plaque including calcium in patients who have femoro-popliteal disease. Subjects will have a baseline visit to determine eligibility for the study, will receive treatment according to this study protocol, and will be followed with office visits at within 30 days, 6 and 12 months after the procedure to collect data. Study participation will be complete when the last study subject enrolled has been followed for 12 months after the procedure.

4.2 Subject Selection

The research coordinator (RC) and IRB-approved study team doctor will have primary responsibility for screening and enrolling eligible candidates. The RC will review NYULMC's Epic system to identify patients with peripheral artery disease from the NYU cardiology practices and patients scheduled for a revascularization procedure in the Cardiac Catheterization Laboratory. The research coordinator will review the medical records to identify the patient and confirm with the principal investigator or Sub Investigator if the patient meets the clinical inclusion and exclusion criteria. If the physician is amenable, the coordinator will approach the patient for a possible consent and enrollment.

Version 23JUL2020 Page 11 of 23

It is expected that approximately 100 participants will sign IRB approved consent in order to accrue 60 subjects to the trial: 30 patients randomized to the OAS arm and 30 patients randomized to the DAS arm.

Once the subject has signed the approved study informed consent form (ICF), and has met all inclusion and no exclusion criteria, the subject will be considered eligible to be enrolled to the trial. Subjects may be either male or female, and must meet all of the inclusion criteria and none of the exclusion criteria in order to be randomized to the either arm of the trial treatment.

4.3 Inclusion Criteria

- Subject's age ≥ 18 years;
- Subject (or Legal Guardian if applicable) is willing and able to provide consent before any study-specific test or procedure is performed, signs the consent form, and agrees to attend all required follow-up visits.
- Chronic, symptomatic lower limb ischemia defined as Rutherford categories 1-4
- Target lesion(s) located in a superficial femoral or popliteal arteries
- Degree of stenosis ≥70% via Qualitative Comparative Analysis (QCA)
- Total Lesion Length ≥ 80 mm and ≤ 250 mm
- Reference Vessel ≥ 3.0 mm and <6.5mm
- Patent infrapopliteal artery, i.e., single vessel runoff or better with at least one of three vessels patent (<50% stenosis) to the ankle or foot with no planned intervention.
- Subject is an acceptable candidate for percutaneous intervention using the OAS or DAS in accordance with their labeled indications and instructions for use

4.4 Exclusion Criteria

Subjects who have an:

- Previously stented target lesion/vessel.
- Subjects who have undergone prior surgery of the SFA/PA in the target limb to treat atherosclerotic disease.
- Presence of aneurysm in the target vessel.
- Interventional treatment is intended for in-stent restenosis at the peripheral vascular site.
- Target vessel with moderate or severe angulation (*e.g.*, > 30°) or tortuosity at the treatment segment that precludes safe advancement of the atherectomy device.
- Pre-planned interventional treatment includes planned laser, brachytherapy or atherectomy procedure other than OAS or DAS.
- Known hypersensitivity or contraindication to contrast dye that, in the opinion of the investigator, cannot be adequately pre-medicated.
- Known hypersensitivity/allergy to antiplatelet, anticoagulant, thrombolytic medications
- Platelet count <80,000 mm³ or >600,000 mm³ or history of bleeding diathesis.
- Patient has any known coagulation disorder, including hypercoagulability
- Receiving dialysis or immunosuppressant therapy.
- Patient has evidence of intracranial or gastrointestinal bleeding within last 3 months.
- Patient has history of severe trauma, fracture, major surgery or biopsy of a parenchymal organ within past 14 days,

- Female patient who is pregnant or nursing a child,
- Current participation in another investigational drug or device clinical study that has not completed the primary endpoint at the time of randomization/enrollment or that clinically interferes with the current study endpoints.

4.5 Data Storage

All subjects who sign the ICF will receive a study ID number. The Subject's source documents and data, under this ID number, will be placed in a subject research binder and inputted into the REDCap database, which is stored on NYULMC's password protected, strongly firewalled server that has been certified by NYULMC's HIPAA Compliance Officer in adherence to DHHS data collection policies. This electronic data storage complies with the FDA Title 21 CFR Part 11 standards for Electronic Records and Electronic Signatures. The subject's research binders will be kept in the secure place in the research office.

5. Study Procedures

5.1 Overview of Data Collection Requirements

Clinical data will be collected upon enrollment at the Baseline Visit, at the time of the procedure, and at within 30 days, and 6 and 12 months after the procedure. Data will also be collected during unscheduled office visits should adverse events connected to the procedure or device occur or should a subject death occur during the 12 months of study follow up after the subject's procedure. Data to be collected includes demographics, medical history, etc. The data requirements are summarized in Table 1.

Data Criteria	Baseline visit	Procedure	Visit 1	Visit 2 (6 mon)	Visit 3 (12 mon)
Compliance Window	30 days prior to procedure	n/a	Within 30 days after procedur e	+/- 30 days	+/- 30 days
Subject Informed Consent	✓				
Inclusion/Exclusion Criteria	✓				
Subject Medical History	✓				
IVUS/DICOM images*		✓			
ABI	✓		✓	✓	✓
Arterial Duplex Ultrasound			✓		√
Rutherford	✓		✓	✓	✓

Version 23JUL2020 Page 13 of 23

Follow-up Visit Form			✓	✓	✓
Adverse Event Form					
Deviation Form	As they occur				
*IVUS/DICOM images to be collected immediately prior to and immediately following use of the OAS/Hawkone and again following Drug Coated Balloon Angioplasty procedures.					

Table 1 Study Data Collection

5.2 Informed Consent

Prior to initiation of any study specific procedures, an IRB approved Informed Consent Form must be signed and dated by the subject. Subjects must be given ample time to review the ICF and have questions answered before signing. The signed Informed Consent Form must be filed in the hospital/clinic medical chart or with the study subject documentation and be available for review by the IRB. A copy of the signed ICF must also be given to the subject for their records. A subject number will be assigned to the subject after the consent has been signed.

5.3 Baseline Visit (Pre-procedure assessments - up to 30 days)

Version 23JUL2020 Page 14 of 23

The following data must be collected within 30 days prior to the index procedure for all subjects:

- Demographics and medical history obtained
- Physical assessment including:
- Weight and height
- Rutherford Clinical Category Assessment
- Ankle-Brachial Indices (ABI) measurements
- Antiplatelet medication usage (if applicable)

5.4 Procedure Visit

Prior to Index procedure the confirmation of clinical assessments of the inclusion and exclusion criteria must have been met. On the day of the procedure, the patient will be prepped for percutaneous intervention per institutional standards.

Patients may be admitted on the day of the procedure for hydration, if deemed medically necessary. Antiplatelet medication should be initiated prior to procedure at a dose deemed appropriate by the Investigator. Investigator will manage the cardiovascular risk factors and comorbidities for all patients according to standard care. Investigator should ensure close monitoring of the amount of contrast for subjects with elevated serum creatinine levels.

Diagnostic angiography of the lower extremities must be performed using standard techniques to confirm angiographic eligibility of the target lesion. Femoro-popliteal arterial lesions intended for treatment at the time of the index procedure that met the inclusion and didn't meet exclusion criteria will be considered target lesions.

Randomization Protocol

A statistician generated list of random treatment allocations (i.e., a randomization schedule) will be used to assign subjects to treatments in a 1:1 ratio of directional atherectomy to orbital atherectomy treatment groups after successfully crossing the target lesion. The randomization assignment sheet will be blinded to the PI.

Index Procedure

After randomization, all subjects will undergo percutaneous revascularization of the femoro-popliteal arteries using a DAS or OAS device and drug coated balloon angioplasty as per the randomization arm.

Adjunctive procedures will be performed at the treating physician's discretion. Use of the same balloon for all dilations is strongly recommended, 1:1 balloon to healthy segment ratio to nominal pressure for at least 3 minutes of duration of balloon inflation.

During the index procedure, the angiographic complications such as emboli, dissections, perforations or abrupt closures will be assessed, treated and recorded as needed.

Intravascular Ultrasound (IVUS)

All patients will undergo at least 3 runs of IVUS:

- a pre-treatment run to assess the severity and morphology of the plaque composition
- a post-atherectomy run to assess changes post atherectomy treatment
- a post drug coated balloon angioplasty (followed atherectomy) to assess changes in overall volumes.

The ruler must be utilized for each procedure for precise measurement of the diseased, treated, and IVUS evaluated segment(s).

The Opticross[™] 18 peripheral imaging catheter (Boston Scientific Corp) is a 6-French (Fr) compatible catheter that performs intravascular analysis of the culprit lesion, measuring grey-scale images over a 0.014″ guidewire. This device is used routinely at the study center.

- 1. Automated pullback (1.0 mm/sec) must be implemented by using the disposable pullback device.
- 2. All pullbacks must be performed at a sufficiently distal point using an external ruler to mark the precise start point.
- 3. Images should be recorded on DICOM format and archived on DVD for off-line analysis.

 Anonymized IVUS images and selected angiograms (pre-treatment view of stenosis, IVUS location and final post-treatment angiogram) will be sent to the Core Laboratory for evaluation.

Adverse Event Collection

Complete SAE collection and assessment

5.5 Follow up.

All randomized/enrolled subjects will be evaluated prior to discharge from the index procedure and continue follow up evaluation at 30 days, 6 months, and 12 months after the index procedure. Requirements of each follow-up evaluation are described below.

Visit 1. 30 days Follow up (within 30 days)

All enrolled subjects must be evaluated within 30 days after the index procedure. The following assessments must be performed during this visit.

- Rutherford Clinical Category Assessment
- ABI Measurements
- Serious Adverse Events collection and assessment
- Arterial Duplex Ultrasound
- Antiplatelet medications assessment

Visit 2. 6 month Follow up (182 days +/-30 days)

All enrolled subjects must be evaluated 6 months after the index procedure. The following assessments must be performed during 6 month office visit.

- Rutherford Clinical Category Assessment
- ABI Measurements
- Serious Adverse Events collection and assessment
- Antiplatelet medications assessment

Visit 3. 12 month Follow up (365 days +/-30 days)

All enrolled subjects must be evaluated 12 months after the index procedure. The following assessments must be performed during 12 month office visit.

- Rutherford Clinical Category Assessment
- ABI Measurements
- Serious Adverse Events collection and assessment
- Arterial Duplex Ultrasound
- Antiplatelet medications assessment

5.6 Unscheduled Visits

An unscheduled follow-up is defined as an office or hospital visit or phone call to the clinic by the subject that is not required by the study protocol but is usually related to an event and occurs between the study baseline visit and 12 months after the procedure. If the subject has an unscheduled follow-up and:

- No serious adverse events noted during unscheduled visit no forms need to be completed
- Serious adverse event noted The Adverse Event CRF needs to be completed for each event

The subject will still be required to return for the next scheduled follow-up visit if the unscheduled visit is out of the compliance follow-up window.

5.7 Trial Completion

The trial will be considered complete:

- after all subjects have completed the 12-month follow-up visit;
- withdrew from the study prior to the 12-month follow-up visit:
- have died:
- or presented at time when the follow-up visit window is closed.

5.8 Study Exit

5.8.a. Lost to Follow-up

Every effort must be made to retain study subjects for the duration of the study. If the subject fails to comply with the protocol requirements to attend the follow up visits, the study center should make at least two attempts to contact the subject. Each of the attempts to contact the subject must be documented in the subject's medical record.

5.8.b. Subject Withdrawal

If the subject chooses to withdraw from the study, the Investigator should attempt to obtain the reasons for the subject's request to withdraw from the study. Once a subject has voluntarily withdrawn, all of the subject's data will be used in the study up to and including the date of withdrawal.

Version 23JUL2020 Page 17 of 23

6. Adverse Events, Deviations & Complaints

6.1 Adverse Events

The only Adverse Events (AE) that will be collected in the study are those events that meet the definition of serious injury, also called a serious adverse event (SAE), which is required for post market surveillance of medical devices by the FDA

6.2. Serious Adverse Event Definitions

Serious Adverse Event (SAE) that:

- 1. Led to a death;
- 2. Led to a serious deterioration in the health of the subject that:
- resulted in a life-threatening illness or injury;
- resulted in permanent impairment of a body structure or a body function;
- or a persistent or significant incapacity or substantial disruption of the ability to conduct normal life functions;
- resulted in in-patient hospitalization or prolongation of existing hospitalization;
- resulted in medical or surgical intervention to prevent permanent impairment to body structure or a body function;
- 3. Led to fetal distress, fetal death or a congenital abnormality or defect.

6.3. Serious Adverse Event Classification

The relationship of the SAE to the atherectomy device will be classified by the investigator.

The investigator will use the following definitions in classifying the relationship of SAE to the study procedures or the medical device:

Device Related: A SAE that is directly related to the atherectomy device.

Procedure Related: A SAE that is directly attributable to the procedure using the atherectomy device. Usually, these events occur within 2 weeks of the procedure.

6.4. Serious Adverse Event Reporting

All serious adverse events must be collected, assessed and recorded on the appropriate eCRF. All relevant source documentation for event will be stored in the subject binder.

Adverse event information will be collected up until each subject's study completion of the trial. All adverse events will be reported as per IRB requirements.

6.5. Study Deviations

A study deviation is defined as an event where the study is not conducted according to the protocol, the study contract, FDA regulations or requirements imposed by the reviewing IRB.

6.6. Product Return, Device Malfunction, and Complaints

In the case of device malfunction, device-related adverse events, compromised product, or complaints, the device is to be returned to the manufacturer. Contact CSI Customer Service at

[name]; or Medtronic Customer Service at 1 [contact] to obtain a Returned Goods Authorization (RGA) number. Every effort should be made to return the device to the Sponsor in a timely manner.

7. Risk Analysis

7.1 Potential Risks and Mitigations

The medical devices used in this study have received clearance by the FDA to be on the market in the US. Therefore, the risk profile is established and there should be no additional risk to the subject due to the use of the OAS/DAS during the procedure as a result of this study.

The risks associated with the endovascular procedure may include, but are not limited to the following:

- Amputation
- Aneurysm
- Arterial dissection
- Arterial perforation
- Arterial rupture
- Arterial spasm
- Arteriovenous fistula
- Bleeding complications
- Death
- Embolism or arterial thrombosis
- Emergency or non-emergency arterial bypass surgery
- Hematoma
- Hypotension
- Infection
- Ischemia
- Restenosis of the treated segment
- Total occlusion of the peripheral artery
- Vascular complications that could require surgical repair

7.2 Potential Benefits

Participation in this study is voluntary. There will be no direct benefits of participating in this study. Information gathered from this study may help with further DAS/OAS development that may benefit future patients who suffers from peripheral artery disease.

Version 23JUL2020 Page 19 of 23

8. Statistical Methods and Data Analysis

8.1 Data Management

Electronic case report forms (CRF) will be used to collect the data from the study. Data will be stored in a secure, password-protected database which will be backed up at periodic intervals to archive data. At the end of the study, data will be archived and retained by NYU.

8.2 Statistical and Data Analysis Methods

The Biostatistician from NYULMC will perform the analysis in collaboration with the Principal Investigator. No interim analyses are planned.

Descriptive statistics will be generated to describe study findings (i.e. subject demographics, plaque volume, lumen volume, vessel size, etc.). The mean differences between pre-procedure and post-procedure measures will be analyzed using paired t-tests. The pre- and post-procedure changes in the primary and secondary outcomes will be compared between the two treatment arms by the Intention to treat (ITT) principle. Multivariable linear regressions will be used to compare the change between treatments adjusting for subject demographics and other covariates. A p-value of \leq 0.05 will be considered to indicate statistical significance.

Group sample sizes of 30 and 30 achieve 80% power to detect a difference of 0.7 standard deviation difference in the mean of the primary outcome between the two groups with a significance level 0.05.

IVUS DICOM Image Analysis

Anonymized IVUS Images and selected angiograms should be recorded on DICOM format and archived on DVD for off-line analysis.

Quantitative assessment of the treated segments will be performed using planimetry echoPlague software (Inedc, Mountain View, CA).

9. Data Safety Monitoring

Due to the fact that this is an investigator initiated trial there will be no external monitoring or auditing for this study. In this study, a Clinical Event Committee (CEC) or a Data Safety Monitoring Board (DSMB) will not be used. The Principal Investigator will conduct interim monitoring of any serious adverse event at the time of occurrence and annually to assure the continuing safety of participants, relevance of the study question, appropriateness of the study protocol compliance and integrity of the accumulating data. The PI in conjunction with NYU IRB will be responsible for monitoring the data and conducting safety reviews every12 months when annual re-approval is sought. During the review process, the PI and NYU IRB will evaluate whether the study should continue unchanged, require modification/amendment, or close to enrollment. This study will not have predefined stopping rules due to the fact that both devices are proven to be safe in multiple clinical trials and approved by FDA for routine clinical practice.

Version 23JUL2020 Page 20 of 23

10. Investigator Records and Reports

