2.4 Study Objectives and Endpoints

2.4.a. Primary Objective

 To investigate the hard and soft plaque removal with directional and orbital atherectomy by analyzing changes in plaque volume and composition and vessel size using IVUS). Freedom from complications, target vessel patency and target lesion revascularization (TLR) at 6 months and one year will also be evaluated.

2.4.b. Primary Endpoint

Acute luminal gain (increase in minimal luminal area via IVUS measurement immediately following atherectomy)

2.4.c. Secondary Endpoints

- Plaque burden reduction. The plaque composition and amount of removed plaque will be analyzed via IVUS.
- Device success (≤ 30% residual stenosis following atherectomy, as measured by angiography, without adjunctive endovascular interventions)
- Rate of procedural angiographic complications such as dissection, perforation, emboli, abrupt closure, need for bail out stenting.
- Major Adverse Event Rate at 30 days post procedure defined as clinical TLR, major unplanned amputation of the treated limb, or all-cause mortality
- Rate of clinical TLR, unplanned amputation of the treated limb, or all-cause mortality at 6 and 12months post index treatment.
- Primary patency at 1 year defined as freedom from target lesion restenosis detected with duplex ultrasound Peak Systolic Velocity Ratio (PSVR) is ≤ 2.4
- Rate of Hemodynamic Improvement as assessed by changes in ABI at 6 and 12 months as compared to post-procedural baseline (i.e., within 30 days).
- Improvement in Rutherford Clinical Category within 30 days, at 6 months and at 12 months, defined as an improvement in clinical status indicated by a decrease of one or more in Rutherford Clinical Category compared to baseline, that is attributable to the treated limb (in cases of bilateral disease).

Version 23JUL2020 Page 10 of 23

3. Investigator Selection and Responsibilities

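### Section 8.2 compares secondary outcomes between arms as pre/post change, using linear regression, but five of the eight have no pre-procedure value, so their analysis is undefined

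*Combined protocol and SAP*

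**What the plan says.** Section 8.2 contains three inferential statements.

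- Within subjects: "The mean differences between pre-procedure and post-procedure measures will be analyzed using paired t-tests".
- Between arms, on an intention-to-treat basis: "The pre- and post-procedure changes in the primary and secondary outcomes will be compared". No secondary outcome is exempted.
- Model: "Multivariable linear regressions will be used to compare the change between treatments adjusting for subject demographics and other covariates". This is the only between-arm model named.

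The Statistical Analysis row of the Protocol Summary gives only the paired t-tests, the 0.05 threshold and descriptive statistics. Neither place gives a method for proportions, ordinal categories, or follow-up that ends early.

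Section 2.4.c lists eight secondary endpoints. Most are worded as rates or as status at a fixed time, for example "Primary patency at 1 year defined as freedom from target lesion restenosis". Section 5.8.b says that after withdrawal a subject's "data will be used in the study up to and including the date of withdrawal". It does not say how that partial follow-up enters a 6- or 12-month rate.

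**The concern.** The between-arm rule names the secondary outcomes and prescribes a quantity, the change from before to after the procedure, that most of them do not possess. An analyst following Section 8.2 literally cannot produce a result for them. Some other analysis would have to be chosen, possibly after the data are seen.

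Section 2.3 says the trial is meant to show whether directional atherectomy is superior to orbital atherectomy, and cites patency and revascularisation as the expected long-term gains. Those outcomes, together with procedural complications and major adverse events, are the ones left without a workable analysis. The nearest substitute within the plan's wording is to put the 0/1 outcome into the linear model. With 30 subjects per arm, that can give misleading intervals when events are few. The 6- and 12-month rates would also depend on an unstated choice about early leavers.

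**Working it through.** **Step 1. Does a pre-procedure value exist?** Endpoints are from Section 2.4.c and assessment times from Table 1 and Sections 5.3 to 5.5.

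| Secondary endpoint | Form | Pre-procedure value? |
|---|---|---|
| Plaque burden reduction | continuous (IVUS) | yes |
| Device success | yes/no | no |
| Procedural complications | yes/no | no |
| 30-day major adverse events | yes/no | no |
| TLR/amputation/death, 6 and 12 months | rate at fixed times | no |
| Patency at 1 year | yes/no (duplex only at Visit 1 and 12 months) | no |
| Hemodynamic improvement | rate built on ABI change | ABI measured at baseline, but the endpoint's reference is post-procedural |
| Rutherford improvement | yes/no, built on change in category | yes |

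Five of eight have no pre-procedure value. The ABI endpoint, as worded, is not a pre/post-procedure change either. It still has a defined change from its own reference, so it is not counted here.

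**Step 2. The plan's own figure.** The only figure in Section 8.2 is the power statement for the primary outcome: "Group sample sizes of 30 and 30 achieve 80% power to detect a difference of 0.7 standard deviation difference in the mean". With 30 per arm, 0.7 SD and α = 0.05, the noncentrality is 0.7 × √(30/2) = 2.71 on 58 df. Power is then 76.0% two-sided or 85.0% one-sided, so the stated 80% is not reproduced. That is a separate matter. No figure is given for any secondary endpoint.

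**Step 3. Substitute: regress the 0/1 outcome on arm.** Unadjusted, this is the equal-variance t-test. The standard error is √(s² × 2/30), where s² = [30p₁(1−p₁) + 30p₂(1−p₂)]/58, and the 95% interval is p₁−p₂ ± 2.002 × SE. All 31 × 31 possible tables were enumerated and weighted by their binomial probabilities. The event rates are assumptions.

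| True rates | Coverage of nominal 95% interval | Probability of no event in either arm |
|---|---|---|
| 1% vs 4% | 77.1% | 21.7% |
| 2% vs 5% | 85.5% | 11.7% |
| 5% vs 10% | 93.0% | 0.9% |
| 5% vs 15% | 93.5% | 0.2% |
| 10% vs 30% | 94.8% | about 0 |
| 70% vs 90% | 94.8% | about 0 |

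When neither arm has an event, s² = 0 and the interval collapses to the single value zero, which misses any true difference. That accounts for 21.7 of the 22.9 points of non-coverage at 1% vs 4%, and 11.7 of the 14.5 points at 2% vs 5%.

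Two-sided type I error of the same test at a common rate is 0.03% at 1%, 2.8% at 5%, 5.4% at 10%, 4.9% at 20% and 5.2% at 50%. The maximum over rates of 1% to 99% is 5.5%.

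**Step 4. One sparse table, 4/30 vs 0/30.**

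- Linear model: s² = 30 × 0.1333 × 0.8667/58 = 0.0598; SE = √(0.0598 × 2/30) = 0.0631; t = 0.1333/0.0631 = 2.11; p = 0.039; interval 0.7% to 26.0%.
- Fisher's exact test: p = 0.112. Newcombe interval: −0.6% to 29.7%.
- Uncorrected chi-square: p = 0.038.

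**Step 5. Early leavers.** Assume a true 12-month risk of 20% at constant hazard, h = −ln 0.8 = 0.223, with a fraction of subjects leaving evenly over the year. A leaver's average chance of an event before leaving is 1 − 0.2/0.223 = 0.104.

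- 20% leave: counting leavers as event-free afterwards gives 0.8 × 0.20 + 0.2 × 0.104 = 18.1%. Dropping those who left without an event gives 0.181/(1 − 0.2 × 0.896) = 22.0%.
- 10% leave: 0.9 × 0.20 + 0.1 × 0.104 = 19.0%, and 0.190/(1 − 0.1 × 0.896) = 20.9%.

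**The case against.** The strongest reply is that the wording is loose rather than wrong. On this view the change methods are meant only for outcomes that have a change, the event endpoints simply have no stated inferential method, and nobody proposes a linear model for 0/1 data. This is partly fair, since no sentence says that yes/no outcomes will be regressed. But the between-arm sentence names the secondary outcomes without exception and ties them to pre/post change. The rule as written cannot be carried out for five of them, and even on the charitable reading they have no method.

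Three stronger readings are tempting, and the documents do not support them.

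- A reader might infer that paired t-tests are prescribed for all secondary outcomes. That sentence refers only to pre- and post-procedure measures. The secondary outcomes enter through the between-arm sentence.
- A reader might infer that some endpoints are defined as time-to-event. All are rates or status at fixed times. Kaplan-Meier is a sensible way to estimate one of them, not something the definitions require.
- A reader might infer that the plan would generally produce wrong p-values. It would not. Type I error of the unadjusted linear model does not exceed about 5.5%, it is conservative when events are rare, and coverage is 93% to 95% at moderate rates. The contrast of 0.039 with 0.112 in Step 4 largely reflects Fisher's conservatism, as the chi-square result shows.

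The early-leaver effect is also modest, about 2 points either way under an assumed 20% loss.

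**Conclusion.** The point holds in this form: Section 8.2 prescribes a between-arm comparison of change, with linear regression as its only model, and that analysis is undefined for five of the eight secondary endpoints. This follows from the documents alone and needs no assumption.

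The numerical consequence is conditional. If the 0/1 outcome were regressed, intervals would fail mainly when events are rare: coverage of about 77% at 1% vs 4% and 86% at 2% vs 5%, mostly because of the zero-width interval when no events occur. These rates are assumed, and the calculation is unadjusted with complete data on 30 per arm. Rates this low are plausible for 30-day major adverse events. Nothing in the documents supports them for device success, complications or patency.

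The primary endpoint, a continuous IVUS change, is not affected. The plan should be amended before analysis, but this does not threaten the main comparison.

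**What to change.** Amend Section 8.2, and align the Protocol Summary, as follows.

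- Limit paired t-tests and linear regression of change to the continuous IVUS and ABI measures, stating the reference time for ABI.
- Compare device success, procedural complications, 30-day major adverse events, Rutherford improvement and 12-month patency as proportions. Use risk differences with Newcombe or exact 95% intervals and a named exact or similar two-proportion test.
- State how a missing 12-month duplex is handled in the patency comparison.
- Estimate TLR/amputation/death at 6 and 12 months by Kaplan-Meier, censoring at last contact, and give the between-arm difference with a 95% interval. This uses data up to withdrawal, as Section 5.8.b intends, on the assumption that leaving is unrelated to risk. State a fallback for an arm with no events, where the usual Greenwood variance is also zero.
- Do not use Kaplan-Meier or a 6-month estimate for patency. Duplex is scheduled only within 30 days and at 12 months, so a curve would mainly trace scan dates.

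The cost is a few sentences of text and a little more analysis work with standard software, and no extra data. Some results that would have been nominally significant may no longer be so, particularly if Fisher's test is chosen.
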